This study will provide us with information about the diagnostic quality of the nutritional screening carried out in our environment compared with the GLIM criteria for malnutrition. In addition, by comparing the prevalence of sarcopenia and the phase angle in patients with positive or negative screening, we will be able to estimate the risk of muscle and cellular dysfunction in patients with the worst clinical prognosis.

Methods

Trial design:

Cross-sectional single-center study comparing the diagnostic quality of the CIPA instrument in the diagnosis of malnutrition or risk of presenting it in hospitalized patients vs GLIM and subsequent prospective follow-up of patients for up to six months.

The aims:

Primary endpoint:

- Determine the diagnostic quality of the CIPA tool, in inpatients with stays longer than three days, in the observation of risk of malnutrition compared to the gold standard GLIM as a diagnosis of malnutrition.

Secondary endpoints:

- Determine the positive and negative predictive values in comparison to the selected gold standard.
- Determine the degree of reliability, likelihood ratio and diagnostic odds ratio of the tool compared to the gold standard.

- Determine the point of greatest balance between sensitivity and specificity for each of the three variables that make up the diagnostic instrument for malnutrition.
- Determine the degree of Kappa concordance between both diagnostic criteria (CIPA vs. GLIM).
- Establish the cut-off point for the phase angle of the population studied by bioimpedanciometry for men and women, and determine prognostic values according to the optimal cut-off point.
- Evaluate prognostic variables (mortality, average stay, readmission rate) according to the two tools under study (CIPA vs. GLIM) at discharge, together with early readmissions, and mortality at six months of prospective follow-up.
- Evaluate whether CIPA positive subjects obtain worse muscle functionality results according to dynamometry than CIPA negative subjects.
- Determine if there is a relationship between positive CIPA and sarcopenia according to established EWGSOP2 diagnostic criteria.
- Determine if there is a relationship between positive subjects with sarcopenia vs negatives in relation to the six-month prognosis.

Inclusion criteria:

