The participation of the patients in the study will consist of performing the screening for malnutrition that is usually used in the hospital (CIPA) to which the GLIM test will be added, considered as the gold standard for this work. The scores of both tests will be recorded together with the data collection through the clinical history or with direct questions to the patient.

For the CIPA test, the BMI, albumin levels and percentage of decreased intake will be taken. For the GLIM test, phenotypic criteria such as non-voluntary weight loss and reduction in muscle mass will also be studied together with etiological criteria to which, in addition to those mentioned for the CIPA test, the presence of inflammation will be added.

Together with the usual work protocols and data depending on the pathology under treatment, the variables collected will be: age, sex, cause of admission, comorbidity, functionality, interventions or treatments per admission, bioimpedance testing, dynamometry, presence of sarcopenia.

Subsequently, the sample of patients with a positive CIPA (as it is currently considered the screening test used in the hospital) will be implemented the therapeutic measures according to the usual protocol, while the subjects with a negative CIPA test but a positive GLIM will be studied. and constant monitoring taking the appropriate measures according to optional criteria. The patients will be followed up for the study of prognostic factors based on the variables obtained.

Statistical analysis of the data:

The data will be recorded in the data recording notebook and imported once the study is closed to specific software for statistical treatment (STATA SE 14; SPSS, V21). The descriptive analysis of the data will divide the variables into qualitative and quantitative. Obtaining means and standard deviations for the quantitative variables and frequencies and proportions for the qualitative data. Graphs will be obtained for a better understanding of the results.

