For the cross-sectional study of the quality of diagnostic criteria between the CIPA instrument and the current gold standard GLIM, a study of sensitivity, specificity, positive and negative predictive values, as well as the likelihood and an estimator of a single value such as the diagnostic odds ratio. In addition, they will determine the best equilibrium points for the three items of the CIPA instrument according to the Youden model, determining in each case the area under the curve (AUC). Likewise, the concordance between both CIPA tests and the GLIM gold standard will be determined by the Kappa coefficient according to Cohen's model. All point estimates will be accompanied by 95% confidence intervals.

For the follow-up study with CIPA positive patients, an initial univariate study of the factors that could determine prognostic levels in the patients will be carried out. These analyzes will be parametric/non-parametric according to the homoscedasticity and normality of the data in each distribution, analyzed by the Kolmogorov-Smirnov test. Subsequently, for the variables with statistical significance or clinical relevance found in the univariate analysis, multivariate models will be carried out with the aim of knowing the one that best fits the data and determining the prognostic factors in the patients studied. The selection of the final model will be guided by the principle of parsimony. Collinearity will be evaluated by the main regression component of the explanatory variables. While

the different models will be compared by the likelihood ratio and the Wald test. The existence of confusion will be evaluated by clinical criteria with a significant change of 10% over the coefficient obtained according to the variables included in the model. The model will be validated by the Hosmer-Lemeshow calibration test and by the area under the curve (AUC) as a measure of discrimination.

Workplan:

This study will select patients with an expected hospital stay of more than three days, through probabilistic sampling to control possible biases in the selection of subjects. The selection will be made in the departments specified by physicians or personnel trained for this purpose, establishing whether they meet all the established inclusion criteria and none of the exclusion criteria, according to the study protocol. Each patient will receive a full explanation of the study objectives and an informed consent form will be signed.

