Once the patient is selected and coded to ensure data protection, after three days of stay, according to the usual protocol, the risk of malnutrition will be studied with CIPA and, later, GLIM will be performed on these patients.

For the evaluation of cell function, the phase angle obtained by bioimpedanciometry (Aker BIA 101 Anniversary) will be used and observing the ratio between reactance/resistance between body cell mass and fat-free mass. Likewise, muscular functionality will be evaluated by dynamometry (using a Jamar dynamometer), taking the maximum value of between two measurements in the dominant arm with an interval of at least one minute between one and the other. In turn, the values under study will be collected and the the data collection notebook according to coding. The risk of sarcopenia will be determined according to values observed in dynamometry and bioimpedance measurement established in the 2019 European consensus on Sarcopenia according to the EWGSOP2 criteria: grip strength determined by dynamometry, positive in males if < 27 kg and in women if < 16 kg, muscle volume, determined by bioimpedance analysis, positive if appendicular skeletal muscle mass < 20 kg in men and < 15 kg in women.

All subjects with a positive test according to the CIPA instrument will be treated according to the usual protocol to correct possible malnutrition or risk thereof,

while subjects with a negative CIPA test but a positive GLIM will be studied and constantly monitored, taking the appropriate measures according to criteria. optional. Patients will be followed up during their hospital stay and 6 months after discharge, prospectively collecting variables for the study of prognostic factors (hospital stay, early readmission rate, mortality).

The study consists of a first cross-sectional part that will be completed once the data of the 490 subjects selected through probabilistic sampling has been collected. The second part of the study will consist of the prospective follow-up of the patients and the variables will be analyzed with prognostic criteria. In these cases, follow-up will end 6 months after discharge. Thus, the total estimated months to complete the study is estimated at 15 months. The study will be conducted entirely at HUNSC.

Difficulties and limitations of the study:

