In previous studies, a slight-moderate correlation has been observed between nutritional screening methods and the GLIM criteria. Boulhosa et al studied patients with advanced chronic liver disease comparing NRS-2002 with GLIM. They obtained a Kappa index of 0.43 and an AUC of 0.731 [16]. Clark et al compared MST vs. GLIM, sensitivity was 56.7%, specificity 69.0%, AUC 0.63, and kappa index 0.26 [17]. For their part, Bellanti et al. compared GLIM with MUST, VGS and NRS-2002 in a sample of 152 hospitalized geriatric patients, obtaining a sensitivity of 64%, 96% and 47%, and a specificity of 82%, 15% and 76%, AUC of 0.80, 0.77 and 0.69, respectively. In turn, the agreement with GLIM was 89%, 53% and 62% for the MUST, VGS and NRS-2002 [18]. The good correlation of MUST with GLIM can be explained by the degree of similarity between the two tests, since the MUST determines the BMI, percentage of weight loss, presence or absence of inflammation or acute diseases, and these parameters are included. inside the lim. Likewise, the high sensitivity of the VGS is due to the fact that it is not a screening method, but a more specific nutritional assessment, such as the GLIM, and where criteria are similar to the phenotypic and etiological ones. In any case, as can be seen, they are different populations in which it is not convenient to compare or combine the findings.

As for sarcopenia, it is also a pathology with a high prevalence. Ballesteros et al. [19] studied hospitalized patients from the Spanish population, determining a

probable prevalence of sarcopenia of 33%, confirmed by determining muscle mass in 22.5%. Lengelé et al [20] observed a higher risk of sarcopenia in patients diagnosed with malnutrition using the GLIM criteria (HR 3.19 (95% CI 1.56 – 6.5) [20] and Bellanti et al [18] observed that patients with a high risk of malnutrition determined by MUST are also more likely to present sarcopenia (OR 2.5, CI 1.3-3.6).

As for the limitations, we find ourselves with an ambitious study in which a large sample is to be recruited, and it may be assumed that the time necessary for the inclusion of the subjects in the study and data collection is delayed. On the other hand, perhaps the representation of patients admitted to surgical areas may be limited since the need for artificial nutrition prior to performing nutritional screening has been included as an exclusion criterion, the need for this being greater in complex surgical patients.

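### The only specified prognostic analysis covers CIPA-positive patients alone, so it cannot meet the objective of evaluating prognosis by CIPA and by GLIM

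*Combined protocol and SAP*

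**What the plan says.** Statistical analysis of the data has two inferential paragraphs. The first covers cross-sectional accuracy: sensitivity, specificity, predictive values, likelihood and diagnostic odds ratios, Youden cut-offs with AUC, and kappa. The second is the only place that gives a method for prognosis: univariate tests, multivariate models, then Hosmer-Lemeshow calibration and AUC. It opens "For the follow-up study with CIPA positive patients, an initial univariate study of the factors that could determine prognostic levels".

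Three secondary endpoints under The aims concern prognosis:

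- By tool: "Evaluate prognostic variables (mortality, average stay, readmission rate) according to the two tools under study (CIPA vs. GLIM) at discharge", with early readmission and six-month mortality added.
- By sarcopenia: "Determine if there is a relationship between positive subjects with sarcopenia vs negatives in relation to the six-month prognosis".
- By phase angle in the studied population: "determine prognostic values according to the optimal cut-off point".

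The follow-up itself is described without a CIPA restriction. Data Collect says "The patients will be followed up for the study of prognostic factors based on the variables obtained". The Workplan says "The second part of the study will consist of the prospective follow-up of the patients and the variables will be analyzed with prognostic criteria", and also that "subjects with a negative CIPA test but a positive GLIM will be studied and constantly monitored". The study variables table lists stay, six-month mortality and six-month readmissions as follow-up items, with no limit to CIPA positives.

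**The concern.** The analysis section restricts the prognostic work to one level of the variable whose prognostic value is to be evaluated. If an analyst follows it literally, the two-tool objective has no CIPA estimate. Its GLIM estimate also omits the patients whom GLIM identifies and CIPA misses. Data Collect and the Workplan single out that discordant group for monitoring. It also bears directly on the Discussion's stated interest in learning when the more demanding GLIM assessment is needed.

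The sarcopenia and phase-angle results would rest on fewer patients and would not describe CIPA-negative inpatients.

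**Working it through.** **Textual check.** The plan gives no figure for the prognostic analysis, so there is none to reproduce. The 490 is the total sample, stated without a derivation.

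1. Objective: outcomes by CIPA and by GLIM. This needs both levels of each tool.
2. Follow-up: patients in general, in Data Collect, the Workplan and the variables table.
3. Specified method: CIPA-positive patients.
4. Is there another method? The descriptive analysis (means, standard deviations, frequencies, proportions) is unrestricted but names no contrast by CIPA or GLIM. The Workplan's sentence on prognostic criteria names no comparison, model or population. No comparative or model-based method for the two-tool objective exists elsewhere.

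**Consequence.** In the set CIPA = positive, the CIPA indicator has zero variance, so no coefficient, risk difference or odds ratio for CIPA can be estimated. GLIM can vary, but any estimate is conditional on a positive CIPA. This needs no assumed figure.

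**Illustration of how many patients are affected.** The documents give neither the CIPA-positive share nor CIPA's accuracy against GLIM, so both are assumed.

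- N = 490 (Workplan).
- GLIM prevalence p = 0.237 or 0.297 (Background). The lower figure is for patients malnourished or at nutritional risk and is not a GLIM prevalence.
- Sensitivity/specificity against GLIM (Discussion): MST 0.567/0.690; MUST 0.64/0.82; NRS-2002 0.47/0.76.

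Formulas:

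- Analysed = N × [p × sens + (1 − p) × (1 − spec)]
- Left out = N − analysed
- GLIM positives left out = N × p × (1 − sens)
- Standard-error ratio = √(N / analysed)

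Example, MUST at p = 0.237: 490 × [0.237 × 0.64 + 0.763 × 0.18] = 141.6 analysed; 490 × 0.237 × 0.36 = 41.8 GLIM positives left out; √(490/141.6) = 1.86.

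| p | Accuracy as for | Analysed | Left out | GLIM+ left out | SE ratio |
|---|---|---|---|---|---|
| 0.237 | MST | 181.7 | 308.3 | 50.3 | 1.64 |
| 0.237 | MUST | 141.6 | 348.4 | 41.8 | 1.86 |
| 0.237 | NRS-2002 | 144.3 | 345.7 | 61.5 | 1.84 |
| 0.297 | MST | 189.3 | 300.7 | 63.0 | 1.61 |
| 0.297 | MUST | 155.1 | 334.9 | 52.4 | 1.78 |
| 0.297 | NRS-2002 | 151.1 | 338.9 | 77.1 | 1.80 |

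So 142–189 patients (29–39% of 490) are analysed and 301–348 are left out. The 42–77 GLIM positives left out are 36–53% of all GLIM positives (1 − sensitivity). The SE ratio assumes equal event rates and exposure distribution in the two sets; it is smaller if events concentrate in CIPA positives.

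**Sensitivity to the assumptions.** VGS is not in the table because the Discussion says it is not a screening method. Its values (0.96/0.15) would give 429–433 analysed and only 5–6 GLIM positives left out. Taking instead the Background's 10–50% malnutrition prevalence as a proxy for the CIPA-positive share gives 49–245 analysed (490 × 0.10 to 490 × 0.50).

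**The case against.** The restriction may be a slip of wording or translation. The same paragraph later speaks of the patients studied, and every description of follow-up is unrestricted. This is plausible, and it means one cannot say that patients will in fact be left out. It does not remove the conflict: the analysis section is what an analyst follows, and no other section overrides it.

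GLIM among screen-positives is also a legitimate question, because the Background describes GLIM as a second step after screening. That is so, and it is a reason to keep the CIPA-positive model. It still does not answer an objective framed around both tools.

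The sarcopenia limb is weaker. Positive in that objective could mean sarcopenia-positive or CIPA-positive. On the second reading the restriction may partly match the objective, so the loss there is conditional on the first. Even on the first reading, sarcopenia can still be tested within CIPA positives, only less precisely and for a narrower population.

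Finally, the borrowed accuracy figures are poor proxies. The Discussion itself says of the studies behind them that "they are different populations in which it is not convenient to compare or combine the findings", and CIPA uses its own set of items. This objection stands in full: the counts show what could be at stake and do not predict CIPA's performance.

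**Conclusion.** The concern holds. As written, the prognostic analysis set defeats a stated secondary objective: the CIPA contrast is not estimable, and the GLIM contrast excludes CIPA-negative patients. That conclusion rests on the text alone.

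The size of the loss is uncertain. The illustrative 142–189 analysed and 42–77 GLIM positives omitted depend on assumed prevalence and borrowed accuracy, and other assumptions move them widely. The primary accuracy objective is untouched. This should be fixed, but it does not threaten the study's main result.

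**What to change.** First, the sponsor should confirm whether all enrolled patients are followed for six months. Then reconcile Statistical analysis of the data with The aims, Data Collect and the Workplan:

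- Define the prognostic analysis set as all enrolled patients with follow-up data; for readmission, those discharged alive.
- Estimate each outcome by CIPA status and by GLIM status. Separate models suffice; a joint model is optional.
- Describe outcomes with 95% confidence intervals in the four CIPA/GLIM cells, without modelling within cells, since the discordant ones may be small.
- State what positive means in the sarcopenia objective, and estimate sarcopenia against six-month outcome in all patients.
- Tabulate nutritional treatment received, already a study variable, by cell. State that the CIPA contrast reflects protocol treatment of CIPA positives, which tabulation does not remove.
- Keep the CIPA-positive model as a labelled subgroup analysis.

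The core of the repair is the analysis set and the two contrasts; the cell and treatment tables are useful additions. If everyone is already followed, the cost is revised wording and modest extra analysis. If the restriction was meant to limit who is followed, six-month follow-up of CIPA negatives is added work.

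### The prognostic model is to be called validated on an AUC and Hosmer-Lemeshow test from the same data that built it, so the AUC will on average be too high

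*Combined protocol and SAP*

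**What the plan says.** The modelling paragraph is in Methods, Statistical analysis of the data. It opens with the population: "For the follow-up study with CIPA positive patients, an initial univariate study of the factors". Selection follows: "for the variables with statistical significance or clinical relevance found in the univariate analysis, multivariate models will be carried out". The aim includes "determining the prognostic factors in the patients studied". Competing models are compared by likelihood ratio and Wald tests, and "The selection of the final model will be guided by the principle of parsimony". The paragraph closes: "The model will be validated by the Hosmer-Lemeshow calibration test and by the area under the curve (AUC) as a measure of discrimination".

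On the data available, the Workplan describes one probabilistic sample of 490 and adds "The study will be conducted entirely at HUNSC". It lists the outcomes when it speaks of "collecting variables for the study of prognostic factors (hospital stay, early readmission rate, mortality". Data Collect does not restrict follow-up to CIPA-positive patients: "The patients will be followed up for the study of prognostic factors based on the variables obtained".

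**The concern.** A model that is screened, selected and fitted on one data set and then scored on that same data set is partly scored on its own noise. Its AUC is apparent performance and exceeds, on average, what the model would achieve in new patients. The Hosmer-Lemeshow test has a parallel weakness here: the coefficients have been tuned to the observations that the test then examines, so it has little chance of revealing overfitting.

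Followed as written, the plan would publish an optimistic AUC, and a calibration test with almost no power against overfitting, under the label *validated*. A reader would take that as evidence that the model works in other patients. The concern covers the binary outcomes (mortality, readmission). It covers hospital stay only if stay is dichotomised.

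**Working it through.** **1. Which data would validate the model?** The document names no split sample, cross-validation, bootstrap, shrinkage or second cohort, and recruitment is at one hospital. That the same data are used is an inference, but no other data set is described. The 95% confidence intervals promised in the diagnostic-accuracy paragraph would express sampling precision and would not remove optimism.

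**2. The plan's own figures.** The only design figure is 490, given without a calculation, so it cannot be reproduced. No AUC, event rate, event count or number of predictors is stated for the prognostic model. Everything below rests on stated assumptions.

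**3. Number of patients (assumed).** The CIPA-positive share is not given. Prevalences quoted in Background serve as stand-ins:
- 490 × 0.237 = 116 (Spanish multicentre study)
- 490 × 0.297 = 146 (later Spanish study using GLIM)
- 490 × 0.50 = 245 (upper end of the quoted 10-50% range)
- all 490, because Data Collect and Workplan follow patients generally

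At 15% and 30% events, 116 patients give 17 and 35 events, and 245 give 37 and 74.

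**4. Number of candidates (assumed).** The variable table has 17 baseline rows. Merging dynamometry with grip strength removes 1, merging weight, height and BMI removes 2, and dropping sarcopenia (derived) and CIPA status (constant among positives) removes 2: 17 − 1 − 2 − 2 = 12. A second value of 18 allows for component variables.

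**5. Simulation.** Independent normal predictors were used, three of them real: weak (log-OR 0.5, 0.4, 0.3 per SD) or strong (0.9, 0.7, 0.5). Candidates were screened by t-test at p<0.05 and a logistic model was fitted. AUC and a 10-group Hosmer-Lemeshow test were computed in the fitting data. There were 1,000 replicates per scenario; the simulation standard error of each mean excess was at most 0.003.

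Excess = apparent AUC − AUC of the same fitted model in new patients.

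Mean excess over fits that selected at least one predictor, and median calibration slope in new patients:

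| n | Excess, strong | Excess, weak | Excess, with elimination* | Fits with apparent > new | Calibration slope |
|---|---|---|---|---|---|
| 116 | 0.05-0.10 | 0.09-0.15 | 0.055-0.12 | 85-99% | 0.35-0.75 |
| 146 | 0.04-0.07 | 0.07-0.13 | 0.04-0.11 | 82-99% | 0.41-0.81 |
| 245 | 0.02-0.05 | 0.04-0.08 | 0.025-0.075 | 75-94% | 0.59-0.89 |
| 490 | 0.01-0.02 | 0.02-0.04 | 0.01-0.04 | 68-88% | 0.77-0.95 |

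*One real and one null predictor forced in, then backward elimination at p>0.05, to mimic clinical relevance and parsimony.

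Examples with 18 candidates and 15% events: weak, n=116, 0.740 − 0.590 = 0.150; strong, n=245, 0.803 − 0.757 = 0.046; weak, n=490, 0.700 − 0.658 = 0.042. Counting fits that selected nothing as zero excess lowers the weak n=116 range to 0.08-0.125.

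Hosmer-Lemeshow gave p>0.05 in 93-97% of fits in every scenario, including those with slopes far below 1.

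**6. Correlated predictors.** A separate simulation used 15 candidates with correlation 0.3, three weak real predictors (0.4, 0.4, 0.3), 10-30% events, logistic screening and backward Wald elimination. For n=116 to 245 the mean excess was 0.04 to 0.14, for example 0.767 − 0.630 = 0.137 at n=116 with 10% events. Hosmer-Lemeshow rejected in 3-7% of fits in the fitting data and 25-50% in new samples. For all 490 at 15% events the excess was about 0.03. With no real predictor, more than half of the runs selected nothing; where a model was selected, mean apparent AUC was 0.60 to 0.72 against a true 0.50.

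**7. Does the bootstrap help?** With 18 candidates, n=116 to 245, and screening repeated in every resample (150 replicates, 60 resamples):

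| Scenario | Apparent | Corrected | New patients |
|---|---|---|---|
| Weak, n=116, 15% | 0.738 | 0.623 | 0.588 |
| Weak, n=146, 15% | 0.732 | 0.630 | 0.594 |
| Strong, n=116, 30% | 0.786 | 0.711 | 0.737 |
| Strong, n=245, 30% | 0.798 | 0.759 | 0.763 |

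Across all nine scenarios run, the corrected AUC missed the new-patient value by −0.026 to +0.036. The uncorrected AUC missed by +0.035 to +0.150.

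**The case against.** The strongest reply is that the model is explanatory. Its declared purpose is to identify prognostic factors, confounding is judged by a 10% change in coefficient, and no listed endpoint promises a risk score or a model AUC. In a translated text, *validated* may mean only that fit was checked in the sample. This stands in part: if the model is explanatory, a change of wording is enough. But the sentence as written presents the AUC as a measure of discrimination under the heading of validation, and readers will take it as performance.

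Hosmer-Lemeshow in the fitting data also has a legitimate use, as a check for lack of fit such as a wrong functional form. The simulations fit the correct form, so a pass rate near 95% is expected. That is fair, and the test can stay as a description. What it cannot support is a claim about calibration in new patients.

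The magnitudes are largely assumed. The prevalence stand-ins are not CIPA results, the lower end of the 10-50% range was not simulated, and the excess runs from negligible to large. If all 490 patients enter the model it is small. All of this stands, and only the direction is firm. Correlation among predictors, a fair criticism of independent draws, did not change the picture.

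Finally, the bootstrap is imperfect when events are few. The error of +0.036 arose with weak predictors and about 22 events (146 × 0.15), but the uncorrected error there was 0.732 − 0.594 = 0.138.

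**Conclusion.** The concern holds. The plan's validation step measures apparent performance, so the AUC is expected to be too high and a passed Hosmer-Lemeshow test says little about new patients. The direction rests only on the plan's text and the absence of any other data. It is an average tendency and need not appear in every data set.

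The size depends on the assumed patient numbers, event rates, candidate counts and effect sizes. It could be substantial if the model uses CIPA-positive patients only, and would be modest if it uses all 490.

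This is a secondary analysis. The search for prognostic factors does not depend on the label, and the primary accuracy analysis and kappa are untouched. The sentence should be changed, but the study's main conclusion is not at risk.

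**What to change.** If AUC or calibration is to be reported as performance, replace the closing sentence of the modelling paragraph with wording such as:

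> Apparent AUC and calibration in the study sample will be reported beside optimism-corrected AUC and calibration slope from bootstrap internal validation (for example 500 resamples), repeating the pre-written variable screening and selection in every resample. Predictors kept for clinical relevance will be listed before analysis and forced in. The Hosmer-Lemeshow test is descriptive.

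State that this applies to the binary outcomes, and whether the model uses CIPA-positive patients only or all 490. The cost is some programming, a written selection rule with less room for judgement, and a lower reported AUC. No new patients or measurements are needed.

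If the model is only explanatory, the minimum change is to replace the claim of validation with a statement that apparent performance in the study sample will be described. That costs a change of wording only.
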